### 10.4 AUTOPSY/DEATH

Copies of the autopsy report and/or death summary must be sent to Edwards as permitted by local laws. This information should be redacted at the site to remove any identifying information (i.e. subject full name, personal identification numbers, address, etc.). Information on the cause of death and valve relatedness will be evaluated by the Principal Investigator.

Deaths which must be reported to Edwards Clinical Affairs Department include:

- All deaths while participating in the study.
- All deaths up to 30 days post study valve explantation.

### 10.5 EXPLANTED VALVES

Every effort should be made to return the explanted valve(s), at autopsy or explantation to Edwards. The explanted valve should be placed in a container with a suitable histological fixative such as 10% formalin or 2% glutaraldehyde immediately after excision and returned to Edwards. Refrigeration is not necessary under these circumstances. Contact Edwards Clinical Research for additional instructions.

Any pertinent information, e.g. operative notes, autopsy report etc should be sent to Edwards. This information should be redacted at the site to remove any identifying information (i.e. subject full name, personal identification numbers, address, etc.).

After the study valve is explanted, the subject will be followed for either an additional 30 days to monitor for any new adverse events or until all study device related serious adverse events (see section 9.1) are resolved. After that point the subject will be discontinued from the study. No further evaluations and/or case report forms are needed after study exit. Data from these subjects will be included in analysis.

## 10.6 PATIENT WITHDRAWAL

The investigator should make every attempt to follow the patient at each of the required assessment periods. This information needs to be indicated on the CRF. Patients may withdraw from the study without penalty or loss of benefits to which they are otherwise entitled. A study patient that has been withdrawn from the study will not be replaced.

## 10.7 MISSED VISIT/ LOST TO FOLLOW-UP

If a subject cannot be reached for a follow-up visit, the investigator will document on the, CRF, the efforts undertaken to contact the subject or the subject's primary health care provider. These efforts should include 3 attempts of telephone contacts at separate dates and times, and a registered letter before the end of the follow-up window. If a subject cannot be reached for the follow-up visit and misses the scheduled visit, the visit will be recorded as a missed visit on the date of last attempted contact. At the next visit interval, the investigator and/or designee will attempt to contact the subject again for follow-up. Should this attempt to contact the subject fail, a family member should be contacted in addition to the subject. Subjects who miss 2 sequential follow-up visits will be considered lost to follow-up at the second missed visit and exempt from future study follow-up visits. After the subject is terminated from the study, the investigator will attempt to determine if the subject is alive; including searching national mortality registries when available and as permitted by local laws.

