#### 4.2.3 PRIMARY EFFECTIVENESS ENDPOINTS

The primary effectiveness endpoint will be:

Proportion of subjects in NYHA Functional Classification I and II at 8 years post-implant.

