## **11.4 EFFECTIVENESS ANALYSIS**

### **Subject functional classification**

Subjects will be stratified according to the NYHA classification preoperatively, at 6 months and annually post implant for 8 years. The distribution (numbers of subjects and percentages) in the various NYHA classes will be tabulated at each follow-up interval.

The primary effectiveness analysis will include all the subjects who survived the implant procedure and have at least one post-implant NYHA assessment. The proportion of the subjects in NYHA Classes I and II at 8 years post implant will be calculated to determine if it is  $\geq 75\%$  using a one-sided Binomial exact test. For subjects who die, withdraw or are lost to follow-up before reaching the 8 year follow-up visit, the last observed NYHA classes will be used in this analysis. As a consequence, those subjects will be counted as failures if they were in NYHA Classes III or IV at the time those events occurred. Subjects whose status at the time of the events is not known will be counted as failures if they were in NYHA Classes III or IV during their last assessment prior to the time of the events.

The proportion of subjects in NYHA Classes I and II and proportion of subjects who died and were in NYHA Classes III and IV at death or at their last known NYHA classification will also be calculated at each annual report.

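### After two consecutive missed visits, Section 10.7 stops seeking everything except vital status, so living subjects who could be reached again have no described way to supply the 8-year NYHA class or later valve events

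*Combined protocol and SAP*

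**What the plan says.** - **Rule for loss (Section 10.7).** A subject who misses two visits in a row is "considered lost to follow-up at the second missed visit and exempt from future study follow-up visits".
- **What is still sought.** "After the subject is terminated from the study, the investigator will attempt to determine if the subject is alive". Mortality registries are to be searched where available. The section describes no re-entry, no later search for events and no 8-year contact.
- **Effort before the rule applies.** For a subject who cannot be reached, sites make "3 attempts of telephone contacts at separate dates and times, and a registered letter before the end of the follow-up window". They try again at the next interval and also contact a family member if that fails.
- **Endpoint (Section 4.2.3).** "Proportion of subjects in NYHA Functional Classification I and II at 8 years post-implant".
- **Primary analysis (Section 11.4).** For subjects who die, withdraw or are lost before the 8-year visit, "the last observed NYHA classes will be used in this analysis".
- **Missing data (Section 11.6).** The effectiveness tests are run on available cases and with last observation carried forward, and the two results are compared.
- **Visits (Section 8.3.2).** 6 months, 1 year, then yearly to at least 8 years.

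**The concern.** The endpoint is read once, at year 8, but the rule can remove a subject many years before that on the strength of two missed visits. A subject who misses years 2 and 3 and is back in contact at year 5 is no longer asked for anything. An intermittent gap thus becomes permanent, and an 8-year class that might have been obtained is replaced by an old one.

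The stake is bias. Subjects who stop attending may do worse than those who keep coming, and carrying forward a class recorded while they were still attending would then flatter the valve. Valve events after termination also go unrecorded, in a study set up to gather long-term data.

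**Working it through.** **1. The plan's own figures (Section 11.1).**
- One-sided exact binomial test, null 75%, expected 90%, alpha 0.05. With n = 45, success needs at least 39; alpha is 0.0446 and power 0.841, against a stated 85%. This reproduces closely.
- P(X ≥ 101 | n = 195, p = 0.60) = 0.992, and 0.990 (0.9896, just short of 99%) with n = 194. The plan's 195 reproduces.
- 195 × 1.15 = 224.25, rounded up to 225.

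**2. How old the carried-forward class can be.** The study procedures chart (Section 2) schedules NYHA class at 6 months and yearly, not at discharge.
- Misses 6 months and year 1: lost at year 1. With no NYHA class after implant (unless from an unscheduled visit), the subject falls outside the primary effectiveness population.
- Attends 6 months, misses years 1 and 2: the class carried to year 8 is at least 8 − 0.5 = 7.5 years old.
- Attends year 1, misses years 2 and 3: 8 − 1 = 7 years old.
- Misses years 7 and 8: the rule costs nothing beyond the missed 8-year visit itself.

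**3. How many subjects.** Inputs: 225 implanted, 60% 8-year survival, loss of 7.8% (seen in the sponsor's earlier study among subjects who reached 5 or more years) or 15% (the plan's ceiling). Applying these rates to all 225, and equally to survivors, is an assumption.
- Lost: 225 × 0.078 = 17.6; 225 × 0.15 = 33.8.
- Expected survivors: 225 × 0.60 = 135. Lost survivors: 135 × 0.078 = 10.5; 135 × 0.15 = 20.3.
- Expected deaths: 225 − 135 = 90. These have no 8-year class to recover.

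**4. Possible bias.** Let g be the gap between the lost survivors' carried-forward rate of NYHA I/II and their true 8-year rate. The documents give no value, so 10 to 40 points is assumed. Overstatement = 0.60 × loss × g. Type I error = P(X ≥ 180 | 225, 0.75 + overstatement), where 180 is the critical value for n = 225. This takes all 225 as analysed, deaths scored as the plan says, and a true overall proportion of 75%.

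| Loss | g | Overstatement (points) | Type I error |
|---|---|---|---|
| any | 0 | 0 | 0.046 |
| 7.8% | 10 | 0.5 | 0.064 |
| 7.8% | 40 | 1.9 | 0.150 |
| 15% | 10 | 0.9 | 0.085 |
| 15% | 40 | 3.6 | 0.338 |

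**5. Power and sample size.**
- With 101 subjects the critical value is 84 and power at 90% is 0.989.
- P(at least 101 survivors with 8-year data from 225), with p = 0.60 × (1 − loss), is 0.999 at 7.8% loss and 0.971 at 15%.

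**6. Safety exposure.** Assume constant hazards: death −ln(0.60)/8 = 0.0639 per year and loss −ln(0.85)/8 = 0.0203, together 0.0842. Expected exposure over 8 years is 225 × (1 − 0.60 × 0.85)/0.0842, or about 1,310 subject-years, well above 808.

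**The case against.** The strongest reply is that few of these subjects may be recoverable. Someone who could not be reached has already had calls, a registered letter, a renewed attempt and a family contact. No figure in the documents says how many would return, and 15% is a ceiling, well above the sponsor's historical 7.8%. The deaths, about 90, supply far more carried-forward values than the losses do. All of this stands, and it limits the size of the point. It does not remove it: the contact steps stop once loss is declared, and neither planned analysis contains the real 8-year class of a lost survivor.

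A reader might infer four stronger claims that the documents do not support.
- **All data collection ends.** Vital status is still sought, and an exemption from visits does not expressly forbid accepting later data. But vital status supplies neither a NYHA class nor valve events.
- **Section 10.7 contradicts Section 10.6.** Section 10.6 says "The investigator should make every attempt to follow the patient at each of the required assessment periods". That is a general duty, and 10.7 is the specific rule for when visits stop being required. They sit uneasily together but can both be followed.
- **The rule breaks a promised 99% probability.** That figure concerns 101 subjects surviving out of 195. The plan does not promise it for 8-year data from 225 after loss.
- **Power or safety exposure is threatened.** Steps 5 and 6 show no such threat.

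**Conclusion.** The point holds as one about avoidable missing data and possible bias in the primary effectiveness result. The plan stops asking for the 8-year outcome in an expected 11 to 20 survivors, some of whom might be reachable later, and describes no way back for them.

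The overstatement of about 0.5 to 3.6 points, and the type I error of about 0.06 to 0.34, depend on the assumed 10 to 40 point gap and on loss applying equally to survivors. They also treat every lost survivor as having a carried-forward value affected by the rule, so they are an upper view of what later contact could correct. With no gap there is no bias. Loss of late valve events is real in principle but cannot be sized from the documents. This is a worthwhile, low-cost improvement; nothing here shows the design to be inadequate.

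**What to change.** Amend Section 10.7 in place of the exemption:
- A subject who misses two consecutive visits and has not withdrawn consent stays eligible, recorded as out of contact.
- Sites repeat the section's existing contact steps at each annual window, or at minimum at the 8-year window.
- A subject who is reached resumes visits.
- At year 8, NYHA class and adverse-event status are sought, in person where possible. Any telephone assessment is flagged and examined in a sensitivity analysis.
- Loss is declared only when the 8-year window closes. The vital-status search stays.

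Cost: a protocol amendment, and a few calls or letters per affected subject per year at existing sites. No extra subjects are needed. The downside is some mixing of assessment mode, since the plan expects follow-up at the hospital and describes no telephone NYHA assessment; the flag and the sensitivity analysis address that.

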# 11. STATISTICAL ANALYSIS

## 11.1 SAMPLE SIZE

Sections 11.1 – 11.3 detail the sample size calculation for the trial as well as the analysis approach for each of the study outcomes. Sections 11.4 and 11.5 address the issues of data

---

PROPRIETARY DATA: This document and the information contained herein may not be reproduced, used or disclosed without written permission from Edwards Lifesciences LLC.

poolability and missing data. Unless otherwise noted, all statistical tests will be performed at 0.05 level.

The sample size calculation for the trial is based on the primary safety endpoints. The linearized yearly rates for thromboembolism, all hemorrhage, all perivalvular leak, and endocarditis will be compared to the OPC provided in FDA's Replacement Heart Valve Guidance. These OPC are presented in Table 6.

**Table 6: Safety OPC**

Adverse Event	OPC
Thromboembolism	2.5
All Hemorrhage	1.4
All Perivalvular Leak	1.2
Endocarditis	1.2

More specifically, a statistical test based on the Poisson [9] distribution will be performed for each of these adverse event rates to evaluate whether it is less than 2 times the appropriate OPC. Thus, the null and alternative hypotheses for each adverse event are as follows:

$$H_0: \lambda \geq 2 \cdot OPC$$

$$H_A: \lambda < 2 \cdot OPC$$

where  $\lambda$  is the linearized yearly rate for the given adverse event (thromboembolism, valve thrombosis, all hemorrhage, all perivalvular leak, and endocarditis) computed when the total subject years reaches 808 and *OPC* denotes the relevant OPC. The test statistic for each adverse event is of the form:

$$Z = (\lambda - 2 \cdot OPC) / \sqrt{\lambda} .$$

$H_0$  is rejected in favor of  $H_A$  if  $Z$  is less than -1.645, the lower 5% percentile of the standard normal distribution. Grunkemeier, et al. [10] have demonstrated that 800 subject life-years is adequate to test against the smallest OPC of 1.2% per subject year (excluding valve thrombosis, and

---

PROPRIETARY DATA: This document and the information contained herein may not be reproduced, used or disclosed without written permission from Edwards Lifesciences LLC.

stratification for major versus minor hemorrhage, and perivalvular leak) with Type I and Type II error controlled at the .05 and .20 levels, respectively.

The proposed subject enrollment is calculated to ensure that at least 101 subjects survive to 8 years post implant. These  $8 \times 101 = 808$  life years in addition to the life years from those subjects not surviving to 8 years will more than fulfill the 800 life-years required by Grunkemeier, et al [10].

Sample size calculation for primary effectiveness endpoint is based on a test of the hypothesis:

$$H_0: p \leq 75\%$$

$$H_A: p > 75\%$$

where  $p$  is the proportion of the subjects in NYHA Class I or Class II at 8 years post implant. The expected proportion of the alive subjects in NYHA class I or II at eight years is above 90%, based on 8 year follow up data for the Carpentier-Edwards PERIMOUNT 2700/2800/2900 valve (this proportion is above 90% within the subjects with valid NYHA assessment at each annual visit till 8 years follow up). Based on this expected proportion, a sample size of 45 subjects provides 85% power to test the hypothesis that the true proportion is greater than 75% using an exact binomial test. Thus, the sample size of 101 subjects with NYHA data at 8 year post implant is more than adequate to provide sufficient power.

The calculated number of subjects ( $n$ ) that must be enrolled in order to have 101 subjects survive to 8 years post implant with 99% probability is based on the binomial distribution. Specifically,  $n$  is such that

$$1 - \sum_{x=1}^{101} \binom{n}{x} p^x (1-p)^{n-x} > 99\%$$

where  $p$  is the probability that a subject will survive for 8 years post implant. This calculation can be performed using standard statistical software. Based on the reported 8-year survival of 60% from Aupart, et al. (2006) [8], a sample size of 195 subjects fulfills the requirements of the equation above. Based on the data collected in a previous post approval study conducted by

---

PROPRIETARY DATA: This document and the information contained herein may not be reproduced, used or disclosed without written permission from Edwards Lifesciences LLC.

Edwards (Study 98-1), a lost to follow-up rate of 7.8% was observed among subjects who reached 5 or more years of follow-up post implant. The sample size is further inflated to 225 to account for up to a 15% rate of lost to follow up.

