## 11.3 SAFETY ANALYSIS

### 11.3.1 PRIMARY SAFETY ENDPOINT

As described above a statistical test based on the Poisson distribution will be performed to investigate whether the linearized yearly rate for each cardiovascular adverse event (thromboembolism, all hemorrhage, all perivalvular leak, and endocarditis) is less than 2 times the appropriate OPC from the 1994 Draft Heart Valve guidance.

For reporting purposes, the percent of subjects who experience an early adverse event within 30 days of implant will be summarized. Linearized rates will be used to summarize adverse events for the late (>30 days) post-operative period. The linearized rates will be reported as the number of events occurring after the early post-operative period per year of subject survival. In addition, the linearized rate and 30-day frequency for thromboembolism will be stratified by concomitant cardiac problems (atrial fibrillation, sinus rhythm, pacemakers, etc.).

Accounting for both early and late post-operative events, actuarial analysis according to Kaplan-Meier will be used to show estimated probability of freedom from each adverse event.

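### The primary safety Z statistic omits subject-years, so the printed pass rule depends on the unit of the rate and does not have the stated error levels

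*Combined protocol and SAP*

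**What the plan says.** Section 11.1 sets H0: λ ≥ 2·OPC against HA: λ < 2·OPC for each primary safety event. The Table 6 OPCs are 2.5 for thromboembolism, 1.4 for all hemorrhage, and 1.2 each for all perivalvular leak and endocarditis. The table gives no unit; the text below it uses percent per subject-year.

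The symbol λ "is the linearized yearly rate for the given adverse event", "computed when the total subject years reaches 808". The statistic has the form Z = (λ − 2·OPC)/√λ, and H0 is rejected if Z "is less than -1.645, the lower 5% percentile of the standard normal distribution".

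The sample-size argument follows: a cited paper is said to show that "800 subject life-years is adequate to test against the smallest OPC of 1.2% per subject year", "with Type I and Type II error controlled at the .05 and .20 levels, respectively".

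Section 11.3.1 gives no other formula. It refers back: "As described above a statistical test based on the Poisson distribution will be performed". It then describes the rates to be reported: "The linearized rates will be reported as the number of events occurring after the early post-operative period per year of subject survival".

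**The concern.** If X events occur in T subject-years, the estimated rate is X/T and its variance is λ/T. The printed denominator is √λ, without T. Follow-up therefore enters the estimate but not its standard error, with two consequences. Z does not follow the standard normal distribution that supplies the −1.645 cut-off. And because the numerator scales with the unit while the denominator scales with its square root, the same data give a different Z per 100 or per 1,000 subject-years.

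This is the decision rule for all four primary safety endpoints. If its meaning is settled after the data are seen, the result can turn on that choice. The literal reading is far too strict. The obvious informal repair, inserting counts, is too lenient, and in a safety test that error favours the device.

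**Working it through.** **Inputs.** T = 808, the OPCs, the margin 2·OPC, the −1.645 cut-off and the error levels .05 and .20 all come from Section 11.1. The true rate under the alternative is not stated; I assume it equals the OPC, and show 0.75 × OPC where noted. Error rates below are exact Poisson probabilities.

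**The plan's 800 life-years.** Null rate 0.024, assumed true rate 0.012, one-sided 5%, power 80%:

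- Normal approximation with both variances: T = [(1.645·√0.024 + 0.842·√0.012)/0.012]² ≈ 836.
- Square-root transform: T = [(1.645 + 0.842)/(2(√0.024 − √0.012))]² ≈ 751.
- Exact Poisson: at T = 811, reject if X ≤ 12; Type I error 4.95%, power 82%.

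The figure of 800 is approximately reproduced. Each of these calculations contains T; the printed Z does not.

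**One data set, several answers.** Take 10 endocarditis events in 808 subject-years (OPC 1.2).

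- Printed Z in % per year: rate 1.238; (1.238 − 2.4)/√1.238 = −1.04. Not rejected.
- Printed Z per 1,000 subject-years: (12.38 − 24)/√12.38 = −3.30. Rejected.
- Counts in the printed form, with 2·OPC·T = 0.024 × 808 = 19.39: (10 − 19.39)/√10 = −2.97. Rejected.
- Null-variance count Z: (10 − 19.39)/√19.39 = −2.13. Rejected.
- Exact: P(Poisson(19.39) ≤ 10) = 0.015. Rejected.

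**Operating characteristics at T = 808.** The expected counts 2·OPC·T are 40.40, 22.62 and 19.39 under the null, and half that (20.20, 11.31, 9.70) if the true rate equals the OPC. Each cell gives the largest passing count, the Type I error, and the power at true rate = OPC.

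| Rule | OPC 2.5 | OPC 1.4 | OPC 1.2 |
|---|---|---|---|
| Printed Z, % per year | 19; 0.01%; 45% | 8; 0.04%; 21% | 7; 0.12%; 25% |
| Printed form with counts, (X − 2·OPC·T)/√X | 31; 7.6%; 99% | 16; 9.4%; 93% | 13; 8.4%; 89% |
| Null variance, (X − 2·OPC·T)/√(2·OPC·T) | 29; 3.8%; 98% | 14; 3.7%; 83% | 12; 5.1%; 82% |
| Exact Poisson | 29; 3.8%; 98% | 14; 3.7%; 83% | 11; 2.9%; 73% |

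At 0.75 × OPC, the printed rule in % per year has power 87%, 53% and 56%; the null-variance rule exceeds 96% for all three OPCs.

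Counts of 20–29, 9–14 and 8–12 pass the null-variance test but fail the printed rule. If the true rate equals the OPC, such a count occurs with probability 52%, 62% and 57%.

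**More follow-up does not help the literal rule.** An observed rate equal to the OPC gives Z = −OPC/√OPC = −√OPC, that is −1.58, −1.18 and −1.10 in % per year. None reaches −1.645 at any T. At 1,600 subject-years, power for OPC 1.2 falls to 9%.

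**The case against.** The best defence is that a count test was meant. The plan calls the test Poisson-based, cites a paper on Poisson variates, gives the statistic only as a form, and fixes the subject-years at which it is computed. With X and 2·OPC·T in place of λ and 2·OPC, the formula is a recognisable Wald statistic. The count-based tests then differ by at most two events, and all reject in the worked example. The text also gives the OPC in percent per subject-year, so a per-1,000 scale is not a live alternative.

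Much of this stands. The power losses belong to the literal reading and do not predict what the trial would do; that reading also errs against the device. But the plan defines λ as a rate, and the charitable reading still misses the stated 5%. With it, 30–31, 15–16 or 13 events pass or fail according to a variance choice the plan does not make. Whether the cited paper supplies a correction cannot be told from the documents.

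Two smaller points are fair. Follow-up may exceed 808 subject-years, because life-years from those who die earlier also count. At an assumed 1,200, the exact test has about 91% power for OPC 1.2. Still, 808 is the analysis point the plan names. And the late-event rule in Section 11.3.1 is introduced for reporting, Section 4.2.2 lists late rates as secondary, and Section 11.2 includes all data up to explant or death. So the primary test probably includes early events, but the plan does not say so.

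**Conclusion.** The concern holds, and the rule must be corrected before it is used. Neither available reading has the stated properties at 808 subject-years. The literal reading in % per year has Type I error of about 0.1% or less and power of 45%, 21% and 25%. The printed form with counts has Type I error of 7.6%, 9.4% and 8.4%. The printed Z is also undefined at zero events.

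The power figures assume a true rate equal to the OPC. The Type I errors need no such assumption, only Poisson counts at 808 subject-years. The 800 life-year target and the enrolment figure are not called into question here.

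**What to change.** In Sections 11.1 and 11.3.1:

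- Define X as the event count and T as the subject-years over which those same events are counted. State whether the first 30 days are in both.
- Name one test in advance: either the one-sided exact Poisson test, rejecting if P(Poisson(2·OPC·T) ≤ X) ≤ 0.05, or Z = (X − 2·OPC·T)/√(2·OPC·T), rejecting below −1.645.
- Give the unit of the OPCs in Table 6, the assumed true rate and the resulting power.

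The cost is wording. Enrolment and the 808 subject-year analysis point need not change. Each test has a small drawback at exactly 808 for OPC 1.2: the null-variance Z has Type I error of 5.1%, and the exact test has 73% power. The latter comes from discreteness: three more subject-years (811) move its cut-off from 11 to 12 events and its power to 82%, with Type I error 4.95%.

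### With subject-years inserted, the primary safety Z test in 11.1 has a true one-sided error of 7.6% to 9.4% at 808 subject-years, not 5%, because its variance comes from the observed rate

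*Combined protocol and SAP*

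**What the plan says.** Section 11.1 sets null and alternative hypotheses for each primary safety event, with the null that the linearized rate λ is at least twice the OPC in Table 6. It announces that "a statistical test based on the Poisson [9] distribution will be performed for each of these adverse event rates". It then prints one statistic, the difference between λ and 2·OPC divided by √λ, and rejects when Z "is less than -1.645, the lower 5% percentile of the standard normal distribution". In this rule λ is the rate "computed when the total subject years reaches 808", so it is an estimate from the data. The section cites a published sample-size result for 800 life-years at the smallest OPC, 1.2% per subject-year, "with Type I and Type II error controlled at the .05 and .20 levels, respectively".

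Section 11.3.1 refers back to this: "a statistical test based on the Poisson distribution will be performed to investigate" whether each rate is below twice its OPC. It gives no other statistic and no other cut-off.

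**The concern.** A cut-off of −1.645 gives 5% error only if Z is scaled by its standard deviation under the null. Here the scale is the observed rate. Rejection is possible only when the observed count lies below its null mean. In that region the square root of the observed count is smaller than the null standard deviation, so Z is pushed too far below zero and the test rejects too often. The bias always favours the device.

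This is separate from the missing subject-years term. An analyst who notices that omission and simply inserts T would still have a test that runs above 5%. All four primary safety conclusions depend on this rule.

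**Working it through.** **Inputs.** From 11.1 and Table 6: OPC 2.5 (thromboembolism), 1.4 (all hemorrhage) and 1.2 (perivalvular leak, endocarditis), read as percent per subject-year; null rate 2·OPC; cut-off −1.645; exposure T = 808. Assumed: events are Poisson. For power, the true rate is taken to equal the OPC, because the plan prints no alternative.

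**1. The plan's own figure.** For the 1.2% OPC, the exact Poisson test first has error ≤ 0.05 and power ≥ 0.80 at 811 subject-years. The null-variance normal formula, T = (1.645·√0.024 + 0.842·√0.012)² / (0.024 − 0.012)², gives about 836. The stated 800 is within 1.4% of 811, so it is reproduced as an approximate requirement. At exactly 800, the exact test passes at ≤11 events, with error 3.2% and power 74.1%.

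**2. The formula as printed, without T.** In percent units at 808 years, the rule passes at ≤7 events (1.2% OPC), ≤8 (1.4%) and ≤19 (2.5%). For example, 7 events give λ = 0.866 and Z = (0.866 − 2.4)/√0.866 = −1.648. The true errors are 0.12%, 0.04% and 0.01%, and power at the OPC is 25%, 21% and 45%. This form is extremely conservative and not workable.

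**3. The formula with T inserted.** With X events, the rate is X/T and its estimated variance is X/T². Hence Z = (X/T − 2·OPC)/√(X/T²) = (X − μ0)/√X, where μ0 = 2·OPC·T. The true error is P(X ≤ c | μ0), where c is the largest count with Z < −1.645. At T = 808:

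| Event | μ0 | Z at c | Z at c+1 | Passes at | True error |
|---|---|---|---|---|---|
| Perivalvular leak, endocarditis | 19.39 | −1.773 (13) | −1.441 (14) | ≤13 | 8.5% |
| All hemorrhage | 22.62 | −1.656 (16) | −1.364 (17) | ≤16 | 9.4% |
| Thromboembolism | 40.40 | −1.688 (31) | −1.485 (32) | ≤31 | 7.6% |

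**4. Isolating the cause.** Replacing √X by √μ0 and changing nothing else gives limits of ≤12, ≤14 and ≤29, with errors of 5.1%, 3.7% and 3.8%. The excess comes from the observed-rate variance.

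**5. Other exposures.** At T = 800 the errors are 9.1%, 6.6% and 6.2%, in the order of the table. Over every whole-year T from 800 to 1,500 they range from 5.7% to 9.9%, with means of 7.5%, 7.3% and 6.7%. They are never at or below 5%.

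**6. Exact Poisson test at 808.** Reject if P(X ≤ x | μ0) ≤ 0.05:

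| Event | Passes at | True error | Power at the OPC |
|---|---|---|---|
| Perivalvular leak, endocarditis | ≤11 | 2.9% | 73% |
| All hemorrhage | ≤14 | 3.7% | 83% |
| Thromboembolism | ≤29 | 3.8% | 98% |

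For the 1.2% OPC at 808, a limit of ≤12 would give error 5.1% and power 82%, so no whole-number limit meets both .05 and .20 there. At 811 years the ≤12 limit has error 4.95% and power 81.6%.

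**The case against.** - **The plan says Poisson.** Sections 11.1 and 11.3.1 both call the test Poisson-based, 11.1 sets a general 0.05 level, and Z is introduced only as a form. An analyst might therefore run an exact test anyway. That is possible, but Z with −1.645 is the only decision rule printed. At 808 years, 12 or 13 leak or endocarditis events, 15 or 16 hemorrhages, or 30 or 31 thromboembolisms pass under Z with T inserted and fail under the exact test.
- **The inflation belongs to a repaired formula.** This stands. A reader might infer that the printed formula itself passes unacceptable valves too often. The documents do not support that: without T, the error is 0.01% to 0.12%. The inflation appears once T is added and √λ is kept.
- **The size depends on exposure.** This also stands. The range 7.6% to 9.4% holds at 808 years. Section 11.1 expects additional life-years from subjects who do not reach 8 years. As an illustration, assume 225 subjects, 60% survival and 15% loss at 8 years, with constant hazards. Retention is 0.60 × 0.85 = 0.51, mean follow-up is 8 × 0.49/(−ln 0.51) = 5.82 years, and exposure is about 1,310 years. The errors are then 7.3%, 6.0% and 6.6%, still above 5%.
- **Power.** A reader might infer that the study is underpowered once the test is valid. The documents do not support that. The 73% is a step effect at one exposure for one OPC value. Three more subject-years give 82%, and the other two OPC values exceed 80% at 808.

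**Conclusion.** The point holds. With subject-years inserted, the only decision rule in the plan has a true one-sided error of 8.5%, 9.4% and 7.6% at 808 subject-years, and above 5% at every whole-year exposure from 800 to 1,500. The stated Type I error of .05 is therefore not met. This rests on Poisson counts, on OPC values read as percent per subject-year, and on λ under the root being the observed rate, as it must be in the numerator. The 800-year requirement is approximately right and is not in dispute. In practice the gap is one or two events per endpoint, but it affects every primary safety conclusion and should be closed before the data are analysed, together with the missing exposure term.

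**What to change.** In 11.1, replace the Z rule by the exact Poisson test on event counts: reject the null if P(X ≤ x | 2·OPC·T) ≤ 0.05, where x is the observed count and T the subject-years analysed. This is equivalent to requiring the exact one-sided 95% upper limit for the rate to lie below 2·OPC. Have 11.3.1 refer to this rule. It supplies the exposure term and corrects the variance in one step. A Z with the null variance would also remove the systematic inflation, but its error can still slightly exceed 5% (5.1% for the 1.2% OPC at 808; at most 5.5% from 800 to 1,500).

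Replace the sentence on Type I and Type II error by the power of the exact test at the exposure that will be analysed, with the assumed true rate stated. An exposure total that rests on assumed survival and loss, such as the 1,310 years above, should not be written in as a fixed figure.

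The change is to wording only; enrolment, follow-up and data collection are unaffected. The pass limit falls by one or two events per endpoint, and the stated power for the 1.2% OPC at exactly 808 years becomes less favourable.
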